3.2. Innovation

Alcohol dependence is very common in BPD and schizoaffective disorder. However, literature on the treatment of these dual-diagnosis populations is quite limited. Thus, the patient population studied is innovative. The drugs tested are also innovative. Each is a dietary supplement with interesting clinical and preclinical properties. In addition, the two treatment options have different mechanisms of action that are relevant to alcohol use disorders and BPD/schizoaffective disorder but have not been the focus of extensive attention. Thus, the proposal is consistent with the NIAAA goal to "Discover, develop, and test new, more effective agents to prevent or reduce drinking" (NOT-AA-14-008). The 2-site clinical adaptive trial design is innovative. Adaptive designs are widely used in some areas of medicine, and are currently being explored in the drug abuse field,¹⁰⁶ but, to our knowledge, have not been used in alcohol research. The design allows for the testing of two treatments as well as an adequately powered trial of the more promising option. The stopping rules are also innovative. If neither of the treatments appears promising, the trial will be stopped. This approach decreases the investment of time and resources should the treatments appear to not be very

effective. If an option is promising then the timeframe for drug development will be faster than with current approaches. We suggest that this approach is consistent with the objective of NIAAA to conduct more efficient clinical trials with novel methodology,¹⁰⁹ and with the specific PA. *Finally, we include an exploratory analysis that will examine, with both medications, whether changes in alcohol use occur before or after changes in alcohol craving, mood or cognition. To our knowledge, such an analysis has not been reported in dual BPD/schizoaffective disorder and alcohol use clinical trials. The findings will help inform whether the effects of the medications on alcohol use are driven by improvement in craving and other clinical outcomes.*

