Weeks 3-12	1000mg BID

Side effects will be managed in a blinded fashion as outlined in Section 3.3.b.11. At weekly visits, the HRSD₁₇, IDS-SR₃₀, YMRS, CSSRS and assessment of alcohol use will again be evaluated. All participants will receive Medical Monitoring (MM) as a psychosocial platform (section 3.3.b.10.). Participants will be paid \$50 at baseline and week 12, and \$30 weeks 1-11. Participants will receive \$5 if they provide the optional DNA blood draw during the Baseline II visit. Participants will also receive a \$2 bonus payment that increases by \$2 each time an appointment is attended and resets back to \$0 if an appointment is missed. Bus or rail passes will be provided when needed. After study completion, participants will be provided standard psychiatric care until outside referral is arranged. If, during Baseline 1, the participant is found to not be eligible for the study, they will receive \$10 for their time.

Figure 1: Timeline for study

Start Up Meeting (Dallas)	٠		
Staff training and inter-rater reliability assessment	•	•	

Inclusion:

- Outpatient men and women age 18-70 years old with bipolar I or II disorder or schizoaffective disorder (bipolar type)
- English or Spanish speaking
- Current diagnosis of alcohol use disorder with at least moderate severity (DSM-5 terminology)
- Alcohol use (by TLFB) of at least an average of 28 drinks a week if male or an average of 21 drinks per week if female and 3 drinking days a week in the 28 days prior to intake
- Diagnosis of substance use disorder other than alcohol, caffeine or nicotine is allowed if 1) alcohol is the self-identified substance of choice and 2) severity of other substance use disorder is ≤ the severity of the alcohol use disorder (DSM-5)
- If diagnosis of bipolar I or II disorder: Patient on a stable dose of a mood stabilizer therapy (lithium, lamotrigine, carbamazepine, oxcarbazepine, or an atypical antipsychotic) for at least 21 days prior to randomization or valproate/divalproex at a stable dose for at least 90 days prior to randomization, or willing to be put on a stable dose of a mood stabilizer prior to the randomization

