- Significant alcohol withdrawal (e.g. delirium tremens) based on clinical judgment. Increases in CIWA-Ar scores will initiate a careful clinical assessment of possible worsening of withdrawal symptoms

Rationale for Protocol Discontinuation Criteria: Discontinuation criteria are designed to ensure the internal validity (e.g. accurate diagnoses) and safety (e.g. acute danger to self or others) of the study.

3.3.b.4. Recruitment and Patient Flow at Referral Sources: Recruitment can be challenging in dual diagnosis studies. By limiting enrollment to the subgroup of people with alcohol dependence who also have BPD or schizoaffective disorder bipolar type, the rate of enrollment is generally not as fast as in studies of patients with alcohol dependence alone. However, in both study sites we have had great success in recruiting this patient population using referral sources we have developed in the communities as well as free and paid advertising. The research team has conducted the largest trials in BPD and substance dependence and have conducted trials that included schizoaffective disorder (bipolar type) in addition to bipolar disorder and substance dependence. These single site studies have enrolled up to 115 participants with BPD and alcohol dependence. Given the inclusion and exclusion criteria in the proposed study both the Dallas and Miami sites conservatively estimate that they can enroll 24 participants each year in the study (48 total). Given these numbers total enrollment will take about 4 years and 2 months.

3.3.b.5. Assessments and Outcome Measures: (see Table 2 for Assessment Schedule) Research coordinators will receive training on the SCID in a 2-day course provided the UT Southwestern Psychiatry Clinical Research Infrastructure (P-CRI) (see resources section for more information on the P-CRI). A half-day reevaluation session will be conducted in years 2, 3, and 4 to maintain diagnostic accuracy. Assessments selected are available and validated in both English and Spanish.

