The primary analysis is to assess between-group differences in alcohol use measures including drinks per drinking day (primary outcome measure), heavy drinking days, and drinking days using Generalized Estimation Equations (GEEs) analysis with a site effect as a cluster. GEE model has been used in a prescription drug abuse treatment study with multiple site adaptive design (Weiss et al., 2010).¹⁰⁶ Point estimates of the difference in the average of the number of drinks per drinking day between treatment groups and their corresponding 95% confidence intervals will be obtained. A similar analysis will be used to assess exploratory aims 1 (mood), 2 (side effects), and 3 (craving). Length of time in the study in weeks will be compared between groups using Cox proportional hazards regression (SAS Proc PHREG). Assessments only obtained at baseline and weeks 6 and 12 (e.g. GGT, AST, ALT and CDT levels) or baseline and week12 (e.g. cognitive assessments, neurosteroid and choline levels) will be analyzed using analysis of variance (ANOVA). The correlation between the reduction in alcohol use/alcohol craving and reduction in manic and depressive symptoms, and also improvement in cognitive outcomes, will be assessed using Pearson's or Spearman's correlation coefficient. To address exploratory aim 6) "Determine whether changes in alcohol craving, mood or cognition occur before or after changes in alcohol use." a panel model with lagged effects¹³⁴ will be used to analyze 12-week longitudinal data (SAS Proc Panel) in order to explore serial correlations between changes in alcohol use and depressive symptoms or cognitive outcomes with lagged effect (e.g. one week, two week). The panel model will be constructed for each alcohol use, alcohol craving, depressive and manic symptom, and cognitive outcome and test if change in alcohol use follows changes in craving, mood or cognition at subsequent visits and vice versa.

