At each stage, a table will show the adverse events (categorized by seriousness, severity, and possible association with study drug) ordered by decreasing frequency for all patients. If appropriate, the incidence rate of adverse events will be compared by Fisher's Exact Test. Special attention will be given to those participants who have discontinued due to adverse events or experienced a serious adverse event. Exploratory analyses such as determining if baseline blood neurosteroid or choline levels predict response and whether changes in these levels are associated with clinical response will be conducted using a mixed model (SAS Proc GLIMMIX) with baseline blood neurosteroid and choline levels as fixed effects. In addition, subgroup analyses with respect to patient demographics and characteristics may be performed as deemed appropriate by the PI and/or biostatistician. Unless otherwise noted, tests of hypotheses are 2-sided and the nominal level of significance will be 0.05.

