3.3.d. Dropouts: Retention is challenging in studies involving BPD/schizoaffective disorder and substance dependence. We have greatly improved our retention over the years by implementing 1) more frequent visits, 2) more frequent contact to remind participants of appointments, and 3) the use of a psychosocial platform. To minimize attrition, we will obtain multiple contact numbers, pay participants small sums at each visit, and to the extent possible have the same research coordinator and psychiatrist assess participants at each visit. In addition, data will be analyzed using an analysis that uses all of the available data and allows for missing data. We will also use a contingency management strategy in which participants are given small vouchers that increase in value with consecutive appointments attended and reset following a missed appointment. We included a similar strategy in a recently completed study in BPD and cocaine dependence (Dallas site) and observed substantial improvement in retention. We anticipate that, using the above approach and considering completion rates in both PI's studies, the proposed study will have a completion rate > 70%. Although we will make every effort to minimize missing visits and dropouts, dropouts and missing visits are common in longitudinal studies. Therefore, we will do comprehensive sensitivity analyses to investigate the consequences of incomplete observations in the analysis of repeated measurement data using local influence, pattern mixture models and multiple imputations.¹³⁵⁻¹³⁷

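### The primary GEE takes the site as its cluster; with only two sites, its standard error, p-value and 95% confidence interval cannot be relied on

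*Combined protocol and SAP*

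**What the plan says.** The Statistical Methods part of Section 3.3.c compares the groups on drinks per drinking day (primary), heavy drinking days and drinking days "using Generalized Estimation Equations (GEEs) analysis with a site effect as a cluster". The same paragraph says that the estimated differences "between treatment groups and their corresponding 95% confidence intervals will be obtained", and it carries a similar analysis to exploratory aims 1 (mood), 2 (side effects) and 3 (craving). Section 3.3.c later states that "tests of hypotheses are 2-sided and the nominal level of significance will be 0.05".

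There are two sites. Section 3.2 says "The 2-site clinical adaptive trial design is innovative", and Section 3.3.b.4 says that "both the Dallas and Miami sites conservatively estimate that they can enroll 24 participants each year".

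The outcome is repeated within participants. Section 3.3.b.1 says of the weekly visits that "CSSRS and assessment of alcohol use will again be evaluated", and Table 2 marks the Timeline Followback at every visit. Section 3.3.d plans sensitivity analyses for "the analysis of repeated measurement data using local influence, pattern mixture models and multiple imputations".

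Nothing in the document names the participant as the GEE cluster. Nor does it give a working correlation, a type of standard error (robust or model-based), a small-sample correction or a reference distribution.

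**The concern.** In a GEE the cluster is the unit taken to be independent of the others, and the standard error is built from variation between clusters. The theory needs many of them, and here the stated cluster gives two. A robust standard error from two clusters has one degree of freedom, yet the usual test treats it as if it were known precisely.

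The unit that does repeat, the participant, is not mentioned. If the analyst falls back on the model-based standard error, about 12 correlated weekly values per person may be counted as nearly independent.

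The primary p-value and 95% confidence interval come from this model. If it rejects far more than 5% of the time under no drug effect, a significant result carries little weight. Section 3.3.c runs the primary efficacy analysis at each stage and considers a confidence-interval approach for choosing arms, so the fault could also affect the interim intervals.

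**Working it through.** **Inputs from the document.** Two sites with equal expected enrolment (24 a year each); weekly alcohol use in weeks 1 to 12, so about 12 post-baseline values; two-sided 0.05; 33 per arm in Stage 1; 100 more at 1:1 in Stage 2, so 33 + 50 = 83 per retained arm; stated power of 81.4% with 66 per arm at effect size 0.50.

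**Assumed, not in the document.** Within-person correlation of 0.3, 0.5 or 0.7; normal outcomes; complete data.

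**1. The plan's own power figure.** For a two-sample t-test with 66 per arm and d = 0.50, the noncentrality is 0.50 × √(66/2) = 2.87 on 130 degrees of freedom. Power is 81.35%, which matches 81.4%. The sample size therefore treats participants as the independent units.

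**2. Robust standard error clustered on two sites.** Let d1 and d2 be the treatment differences in the two equal sites.
- Estimate: (d1 + d2)/2.
- Sandwich variance: the two site contributions are ±(d1 − d2)/4, so the variance is 2 × (d1 − d2)²/16 = (d1 − d2)²/8.
- Wald statistic: √2 × (d1 + d2)/|d1 − d2|, which under the null is √2 times a t variable with 1 df.
- Type I error at 1.96: P(|t₁| > 1.96/√2) = 39.8%.
- With a K/(K−1) = 2 variance correction: P(|t₁| > 1.96) = 30.0%.

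Neither result depends on the assumed correlation or the number of participants.

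**3. Model-based standard error on weekly rows, ignoring within-person correlation.** The design effect is 1 + 11ρ and the type I error is 2Φ(−1.96/√(1 + 11ρ)).

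| ρ (assumed) | Design effect | Type I error |
|---|---|---|
| 0.3 | 4.3 | 34.5% |
| 0.5 | 6.5 | 44.2% |
| 0.7 | 8.7 | 50.6% |

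**4. Simulation under no drug effect.** 4,000 trials per setting, two equal sites, 12 weekly values, tested at |z| > 1.96. Arm sizes are even numbers so that arms split equally within sites.

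| Per arm | ρ | Robust, clustered on site | Robust, clustered on participant |
|---|---|---|---|
| 34 | 0.3 / 0.5 / 0.7 | 40.7 / 39.3 / 38.8% | 6.3 / 6.6 / 5.8% |
| 66 | 0.3 / 0.5 / 0.7 | 40.8 / 41.0 / 41.3% | 5.5 / 5.6 / 4.7% |
| 82 | 0.3 / 0.5 / 0.7 | 39.5 / 38.6 / 39.2% | 5.1 / 5.7 / 5.0% |

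At 82 per arm and ρ = 0.5 the true standard error is 0.115. The site-clustered one has median 0.055, with a 5th to 95th percentile range of 0.005 to 0.161.

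A cross-check with a standard GEE routine (600 fits, 82 per arm, ρ = 0.5) gave 41.0% for site-robust, 48.5% for model-based with site as the group, and 4.7% for participant clusters with exchangeable correlation.

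**5. A 1-df reference (critical value 12.71).** Type I error is P(|t₁| > 12.71/√2) = 7.1% without the variance correction (6.5% to 8.2% simulated) and 5% with it. Simulated power at d = 0.50 with 66 per arm, without the correction, is 24.4%. Participant clustering on the same design gives 82.9%.

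**The case against.** The strongest reply is that the sentence is loosely worded. A site effect is normally a model term, and the authors may have meant site as a factor in a GEE with repeated measures on participants. The power figure and the repeated-measurement language in Section 3.3.d both fit that reading, and such a model would be sound. But no text says so, and the sentence names site in the role of cluster, which is what a programmer would implement.

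Second, the model-based error of 34% to 51% requires weekly rows. If each participant contributed one average, the model-based test would be about right: 4.9% at 83 per arm and 5.5% at 33 in a separate null simulation. This stands as a limit on that branch. It does not help the site-robust test, which stays at 40%. The plan also points to weekly rows: Section 3.3.c assigns ANOVA to measures taken only at baseline, week 6 or week 12, and Section 3.3.d uses all available data.

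Third, 39.8% is one result among several unspecified choices. That is fair, and the range is shown: 30.0% with a variance correction, and about 5% to 8% with a 1-df reference, at the price of the planned power.

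Fourth, the interim stop and drop rules use effect-size thresholds (0.25 and 0.50), not a p-value. The point estimate is not made invalid by the cluster choice, so the interim is exposed only through the interval-based part of treatment selection.

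**Conclusion.** The concern holds. Followed as written, with the usual normal reference, the primary test at a nominal 5% has a true type I error of 30% to 40% with site-clustered robust errors. With model-based errors on weekly rows it is 34% to 51%. The 95% interval then covers the truth in only about 49% to 70% of trials (100% minus those error rates). The robust figures need only two sites of equal size. The model-based figures also rest on the assumed correlations of 0.3 to 0.7 and on weekly rows. Dropout, skewed drinking data and arm selection at the interim were not modelled. The fault is in the standard error, p-value and interval, not in the estimated difference. It must be corrected because the trial's main conclusion depends on this one sentence.

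**What to change.** Rewrite the primary-model sentence in Section 3.3.c so that:
- the participant is the cluster (the repeated-measures subject) for weekly drinks per drinking day; a likelihood-based mixed model for repeated measures would also serve;
- treatment, week, site and the baseline-drinking randomization stratum are fixed effects;
- the working correlation, type of standard error, reference distribution and any small-sample correction are stated; a correction is worth considering at the interim, where participant clustering ran at 5.8% to 6.6% with 34 per arm;
- the primary contrast is the treatment difference averaged over the follow-up weeks, stated explicitly if a treatment-by-week term is included.

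Apply the same specification to heavy drinking days, drinking days and exploratory aims 1 to 3. Make the change before any unblinded analysis. It costs a few lines of the analysis plan and a change to the subject argument in the code, with no extra participants or data. The stated power, which already assumes independent participants, is kept.

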Among participants with alcohol use disorder (in addition to cocaine), and active alcohol use at baseline (n=14), potentially meaningful changes in alcohol use and craving were observed. Citicoline-treated patients had a significant decrease in alcohol craving based on a 0-100 mm visual analogue scale (-28.7±31.3, p=0.05) while the placebo-treated group showed a much smaller decrease in alcohol craving (-1.9±66.4, p=ns). Despite modest baseline values, alcohol use decreased by 0.9 ± 1.4 days/week in the citicoline group as compared to only 0.4 ± 0.9 days/week with placebo. Heavy drinking days decreased by 0.9 ± 2.1 (p=0.04) days with citicoline as compared to 0.0 ± 0.6 with placebo. Drinks per drinking day decreased by 2.4 ± 11.3 with citicoline and 0.8 ± 2.6 with placebo. In the alcohol use group, RAVLT delayed recall performance increased by 12.4 ± 12.9 points with citicoline (p=0.04), but decreased by 1.8 ± 3.5 points with placebo (Cohen's d = 1.5, large effect size). Significance: Findings suggest reductions in both cocaine and alcohol use with citicoline. Memory improved with citicoline, particularly in those with alcohol use. Citicoline was safe and well tolerated, and was associated with better study retention than placebo.

Pilot Study 2: A 12-week, double-blind, placebo-controlled trial of citicoline add-on therapy in patients with BPD I disorder and cocaine abuse/dependence

Methods: 130 outpatients with BPD (depressed), cocaine dependence and a cocaine-positive urine at baseline were given citicoline or placebo add-on therapy to stable doses of mood stabilizers. Both groups received cognitive behavioral therapy and a contingency management plan of escalating payments for each urine sample provided. These payments were not related to whether the urine drug screen (UDS) was positive. **Results:** Among those with at least one post-baseline visit (n=60 citicoline, n=61 placebo) a group (f=4.5, df=1,1057, p=.0351) and group by time interaction (f=11.2, df=1,1057, p=.0009) was observed. Similar results were observed when imputing missing data as cocaine-positive [treatment group effect (p=.0222), treatment group by time effect (p=.0151)]. Completion rates non-significantly favored citicoline (71% vs. 57%).

In those with alcohol dependence, citicoline (n=33) showed a trend toward a greater decrease in days per week of alcohol use than placebo (n=37) (-3.67±4.11 days vs. -1.86±4.44 days, p=.084).

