Results: In participants with at least one post-baseline visit (n=73), a significant group by visit effect for the HRSD was observed (f=2.61, p=0.025). Depression remission rates were greater in the pregnenolone group (61%) compared to the placebo group (37%), as assessed by the IDS-SR (χ 2(1)=3.99, p=.046). Significant baseline to exit changes in pregnenolone, allopregnanolone and pregNANolone levels were observed in the pregnenolone group but not in the placebo group. In the pregnenolone group, baseline to exit change in the HRSA correlated negatively with changes in allopregnanolone (r=-0.43, p=.036) and pregNANolone (r=-0.48, p=.019) levels. Pregnenolone was well tolerated. Side effects and retention were similar in the two groups.

Due to inclusion and exclusion criteria, people with current active AUD were excluded. However, a total of n=5 for pregnenolone and n=8 for placebo with a history of AUD were enrolled. Among these participants, 50% in the placebo group relapsed to alcohol use during the study as compared to only 28% in the pregnenolone group.

Significance: The data, when combined with our prior pilot study, suggest that pregnenolone decreases depressive symptom severity in BPD. Pregnenolone therapy was associated with significant increases in the GABAergic neurosteroids pregNANolone and allopregnanolone that correlated with improvement in anxiety. We have previously reported extraordinarily high rates of anxiety disorders (e.g. 57% generalized anxiety disorder, 54% panic disorder) in BPD and alcohol dependence.¹¹⁰ *Although, few participants had alcohol use disorders, the data suggest lower relapse rate with pregnenolone than with placebo.* Thus, relationships between improvement in anxiety and increases in neurosteroid levels may be clinically important in this dual diagnosis population.

3.3.b. Experimental Study Overview: A 12-week, randomized, double-blind, parallel-group, placebocontrolled adaptive design study of citicoline and pregnenolone is proposed in 199 persons with alcohol use disorder and bipolar I or II disorder or schizoaffective disorder, bipolar type. The primary aim will be to assess change in alcohol use (drinks per drinking day-primary outcome measure) by the Timeline Followback (TLFB) method.^{111, 112} Biomarkers of alcohol use, alcohol craving, mood and cognition will also be assessed. Relationships between neurosteroid and choline levels and the outcome measures will be explored.

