respectively, and the limit of detection was 1 pg for both. With participant consent, DNA will also be obtained for future analysis. Plasma samples for DNA will be coded and sent to UT Southwestern McDermott Center for Human Growth and Development. Samples will have their DNA banked in a secure freezer with coded identification that will not include any personal identifiers such as the subject's name. Samples will begin to be analyzed when 50% (100) have been collected. When candidate genes have been suitably refined, and SNP chips become commercially available, appropriate pathways and candidate genes will be assessed via SNP chips and associated with previously assessed behaviors, personality styles, and/or biologic responses. *The neurosteroid and choline levels are essential as biomarkers and predictor of clinical response, as well as to address exploratory aim 5.*

3.3.c. Statistical Analyses Plan

Randomization: A statistician will randomize participants, stratifying by baseline drinks per drinking day of ≥ 8 and < 8 (based on use patterns in our prior studies).

General Analytic Plan: This is a study utilizing a two-stage adaptive trial design with one planned interim analysis (at end of the first stage). Two stages consist of a treatment selection stage (Stage 1) and a stage of early efficacy confirmation of the selected treatment(s) (Stage 2).¹³¹ In **Stage 1**, participants will be randomized at a 1:1:1 ratio to receive one of the three treatments: placebo, citicoline, and pregnenolone. After 99 participants have completed the duration of treatment (completer, dropout, discontinued) an interim analysis will be performed based on the number of drinks per drinking day (primary outcome measure). Based on the interim analysis, adaptations such as stopping the trial early, re-estimating the sample size, or a different randomization scheme may be applied as recommended by the independent DSMB.

Note that a precision analysis (i.e., a confidence interval approach) will be considered for treatment selection at Stage 1.¹³¹ To evaluate the relative risk of making wrong decision and increase confidence in not making wrong decision at Stage 1, sensitivity analyses based on predictive confidence interval of the true difference, which is calculated using the observed difference, at interim analysis will be conducted for treatment selection. At the end of Stage 1, one of the following decisions will be made based on the following principles:

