At Stage 1, we will recruit 99 subjects (i.e., 33 subjects per arm) with 1:1:1 treatment allocation ratio, which provides clinically meaningful minimum *effect size of 0.25 between each treatment arm and placebo with* a two-sided test at the 5% level of significance. After review of interim data, an additional 100 subjects at 1:1 ratio will be recruited at Stage 2. If the effect size for *both* medications is at least 0.50 at interim analysis then we will have 81.4% power with 66 participants per arm and the study will continue with three treatment arms. To summarize: 1) If neither treatment has an effect size of at least 0.25 at interim analysis then the trial is discontinued. *This effect size was selected because it is a clinically meaningful value. Naltrexone has an average effect size of approximately 0.15-0.20 in clinical trials for alcohol dependence.*¹³³ *Thus, a useful new treatment for alcohol dependence should at least have a larger effect size than the standard treatment. This effect size of 0.25 is also an effect size at interim analysis that provides a reasonable likelihood of a significant difference from placebo at study completion assuming some increase in effect size as more participants are*

enrolled and the variance of the data decreases. 2) If one treatment has an effect size of at least 0.25 then the trial continues dropping the less effective treatment (two-arm study of one medication vs. placebo). 3) If both treatments have an effect size of at least 0.50 then neither treatment is dropped and the trial continues as a three-arm trial (both medications vs. placebo). This assumes that the DSMB assessment determines that the selected treatment(s) has an adequate safety and tolerability profile to continue the trial. We anticipate that the interim analysis will take place at approximately month 26 of the study. As an incentive to enroll quickly and avoid prolonging the study, we will mandate that an interim analysis take place by month 34 even if fewer than 99 participants have been enrolled. All interim analysis decisions will be made in consultation with the NIAAA program official and DSMB.

Statistical Methods:

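### The primary GEE names no baseline-drinking or stratum term although randomisation is stratified on baseline drinking: a free efficiency gain, whose size depends on a correlation that the documents do not give

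*Combined protocol and SAP*

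**What the plan says.** Under Randomization in section 3.3.c: "A statistician will randomize participants, stratifying by baseline drinks per drinking day", cut at 8. Under Statistical Methods, alcohol use measures are compared between groups "using Generalized Estimation Equations (GEEs) analysis with a site effect as a cluster", and the result reported is "Point estimates of the difference in the average of the number of drinks per drinking day between treatment groups" with 95% confidence intervals. Neither baseline drinking nor the stratum is named there or anywhere else for this model.

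The plan does name model terms in other places. Section 3.3.b.10 says that unscheduled crisis sessions and extra contacts will be adjusted for. The exploratory mixed model is specified "with baseline blood neurosteroid and choline levels as fixed effects".

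The form of the outcome is left open. Section 3.3.b says "The primary aim will be to assess change in alcohol use", and Pilot Study 1 reports change ("Drinks per drinking day decreased by 2.4 ± 11.3 with citicoline"), while Statistical Methods compares averages.

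Baseline drinking is always available. TLFB is scheduled at both baseline visits (Table 2), and entry requires an average of "3 drinking days a week in the 28 days prior to intake", so drinks per drinking day is defined for every participant in that window.

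**The concern.** Stratifying on baseline drinking treats it as prognostic. If the model then ignores it, the arms are balanced on baseline but the standard error does not reflect that balance. Tests are conservative and intervals wider than necessary. What is at stake is power and precision that data already collected would supply, mostly at small effects such as the plan's own minimum of 0.25.

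There is a secondary effect on the interim rules. The 0.25 and 0.50 thresholds are standardised effects, and the plan does not say whether the SD is that of follow-up drinking, of change, or of the residual after adjustment.

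**Working it through.** **Inputs from section 3.3.c.** Two-sided 5% level. Effect size 0.50 with 66 per arm if both drugs continue. Stage 1 has 33 per arm and Stage 2 adds 100 at 1:1, so the two-arm path has 33 + 50 = 83 per arm. Minimum effect size 0.25.

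**Assumed, because the documents do not give them.** Baseline-to-follow-up correlation r = 0.2 to 0.7; an even split between strata; normal outcomes with equal SDs; a participant-level standard error; complete data; no interim selection.

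**Step 1: the plan's own figure.** The plan states that if the effect size for both drugs "is at least 0.50 at interim analysis then we will have 81.4% power with 66 participants per arm". With m = d√(n/2) = 0.50 × √33 = 2.872, a two-sample t-test on 130 df gives 81.35%, which matches. The normal approximation gives Φ(2.872 − 1.96) = 81.9%. The planned power is therefore that of a test with no covariate.

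**Step 2: unadjusted test under stratified allocation.** An even split on a normal baseline explains 0.637 of the baseline variance, so the true standard error is k = √(1 − 0.637r²) times the one used.
- Type I error is 2{1 − Φ(1.96/k)}. With k = 0.971 / 0.917 / 0.830 at r = 0.3 / 0.5 / 0.7, this is 4.4 / 3.3 / 1.8%. Simulation at 83 per arm gave 4.4 / 3.5 / 1.8%.
- Power is Φ((m − 1.96)/k).

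**Step 3: continuous baseline in the model.** The residual SD falls to √(1 − r²), so power is Φ(m/√(1 − r²) − 1.96). Simulated type I error is 4.9 to 5.1%.

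**Step 4: results** (m = 2.872, 3.221 and 1.611 for the three blocks).

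| n per arm, d | r | Unadjusted | With baseline | Gain (points) |
|---|---|---|---|---|
| 66, 0.50 | 0.2 | 82.2% | 83.4% | 1.2 |
| | 0.3 | 82.6% | 85.3% | 2.7 |
| | 0.5 | 84.0% | 91.3% | 7.2 |
| | 0.7 | 86.4% | 98.0% | 11.6 |
| 83, 0.50 | 0.2 | 89.9% | 90.8% | 0.9 |
| | 0.3 | 90.3% | 92.2% | 1.9 |
| | 0.5 | 91.5% | 96.1% | 4.5 |
| | 0.7 | 93.6% | 99.5% | 5.9 |
| 83, 0.25 | 0.2 | 36.2% | 37.6% | 1.4 |
| | 0.3 | 35.9% | 39.3% | 3.3 |
| | 0.5 | 35.2% | 46.0% | 10.8 |
| | 0.7 | 33.7% | 61.6% | 27.9 |

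Gains are taken before rounding. With an 80/20 split they change little: 2.9 / 7.8 / 12.8, then 2.0 / 5.0 / 6.9, then 3.3 / 10.5 / 27.2 points at r = 0.3 / 0.5 / 0.7.

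**Step 5: precision.** The confidence interval shrinks by √(1 − r²) = 0.95 / 0.87 / 0.71. The matching sample-size multiplier 1/(1 − r²) = 1.10 / 1.33 / 1.96 makes 66 per arm worth 73 / 88 / 129.

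**Step 6: which term does the work.** Simulated power at 66 per arm and d = 0.50 is 83.6 / 87.6 / 93.0% with the stratum only, 84.6 / 91.0 / 98.0% with continuous baseline only, and 84.4 / 90.8 / 97.9% with both. The continuous value carries the gain, and adding the stratum costs nothing measurable.

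**Step 7: the thresholds.** A true effect of 0.25 follow-up SDs reads as 0.25/√(2(1 − r)) = 0.21 / 0.25 / 0.32 change-score SDs, or 0.25/√(1 − r²) = 0.26 / 0.29 / 0.35 residual SDs.

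**The case against.** The strongest reply is that silence is not a specification. Statistical Methods gives the GEE one clause, with no time term, link, working correlation or covariate list. TLFB is collected at both baseline visits and weekly, and the team reports earlier trials as group-by-time or group-by-visit effects. A longitudinal GEE with baseline among the repeated responses would already use baseline data, and the gains above would then use the wrong comparator. This stands. It limits what can be counted, and it also shows that the model has to be written down.

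The limits on size also stand. The correlation is assumed, and at 0.2 there is little to gain. The 66-per-arm case applies only if both drugs reach 0.50 at the interim. On the two-arm path at d = 0.50 the gain is about half, because unadjusted power is already 90% or more.

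The figures also ignore selection. A null simulation that keeps the better drug and applies the 0.25 stop gave unconditional rejection of about 2.7 / 2.0 / 1.3%, against 4.4 / 3.3 / 1.8% for the fixed-sample comparison. The tables compare two models; they are not operating characteristics of the whole design.

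A reader might infer more, in three ways that the documents do not support:
- **That the primary analysis is invalid.** With a participant-level standard error, the unadjusted follow-up analysis errs on the conservative side.
- **That the omission breaks the stated power.** With complete data the unadjusted follow-up analysis still reaches 81.4% under every correlation shown.
- **That the trial will analyse an unadjusted change score.** That would have only 69.5% power at correlation 0.3 (d = 0.50, 66 per arm), but the plan mentions change only in its aim and its pilot results, and never says that the model uses it.

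**Conclusion.** The point holds as an efficiency improvement, not as a validity defect. The plan stratifies on a variable that it measures for everyone and never places in the primary model. Under the assumptions listed, continuous baseline gains about 2-3 / 7 / 12 points at d = 0.50 on the three-arm path. On the two-arm path it gains about 2 / 4 / 6 points at d = 0.50, and about 3 / 10-11 / 27-28 points at d = 0.25, for correlations 0.3 / 0.5 / 0.7. At 0.2 it gains about 1 point.

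These figures apply only once the standard error is computed at participant level. The text as written clusters on two sites; that is a separate matter to be settled first, and a covariate does not repair it. They also do not apply if baseline is already modelled as a repeated response.

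**What to change.** Under Statistical Methods in section 3.3.c, add to the primary model:
- continuous pre-randomisation drinks per drinking day, from a named baseline TLFB window;
- the randomisation stratum (8 or more / fewer than 8).

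If baseline is instead meant to be a repeated response, say so. Use the same model at the interim and final analyses, and state which SD standardises the 0.25 and 0.50 thresholds. Fix all of this before the interim analysis, so that the covariates cannot be chosen after unblinded results exist.

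The cost is a few sentences in the SAP. No new data or visits are needed.

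Three matters are separate and need their own text: the clustering unit, which on-treatment weeks define the outcome, and how weeks with no drinking day are handled.
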